# 8. Duties of the investigator

## 8.1. Investigator's confirmation

This trial will be conducted in accordance with the protocol, International Conference on Harmonisation Good Clinical Practice E6 (ICH-GCP E6 (R2)) and the current version of the Helsinki Declaration.

All protocol modifications must be documented in writing and implemented only with ethical approval. A protocol amendment can be initiated by either the sponsor-investigator or any investigator. The investigator will provide the reasons for the proposed amendment in writing and will discuss with the Sponsor-Investigator. Any protocol amendment must be approved and signed by the Sponsor-investigator and must be submitted to the appropriate Independent Ethics Committee (IEC) for evaluation and approval, in accordance with local requirements, and to regulatory agencies if required. Approval by IEC must be received before any changes can be implemented, except for changes necessary to eliminate an immediate hazard to trial subjects, or when the change involves only logistical or administrative aspects of the trial, e.g. change of telephone number(s).

### 8.2. Damage coverage

A general liability insurance of the Swiss TPH is in place (Winterthur Police Nr. 4746321). Clinical trial compensation insurance is set up with the LAO-VIET insurance company (Policy 021805872). Another policy will be issue in Cambodia.

#### 8.3. Project management

The trial team will include the PI ([name]), a co-investigator and physician ([name] Laos, [name] in Cambodia), a co-investigator ([name]), a trial statistician ([name]) and laboratory technicians. [name], [name], [name] will be responsible for staff management, communication with the collaborative group, recruitment monitoring, data management, safety reporting, analysis, report writing and dissemination of the trial results. [name] has the main medical responsibility and is responsible for supervision of the lab- and field technicians, staff management, recruitment monitoring, supply of the material, contact to the local authorities and participating institutions.

The investigator team is responsible for ensuring that the protocol is strictly followed. The investigator should not make any changes without the agreement of the principal investigator and the co-investigators, except when necessary to eliminate an apparent immediate hazard or danger to a study participant. The investigator will work according to the protocol and GCP. The investigator may take any steps judged necessary to protect the safety of the participants, whether specified in the protocol or not. Any such steps must be documented. During the treatment the records are maintained by the responsible medical doctor. All entries have to be made clearly readable with a pen. The investigator must be thoroughly familiar with the properties, effects and safety of the investigational pharmaceutical product.

# 9. Ethical considerations

## 9.1. Independent Ethics Committee (IEC)

The study will be submitted for approval by the institutional research commission of the Swiss TPH and the ethical committees of Switzerland, Laos and Cambodia. The study will be undertaken in accordance with the Declaration of Helsinki and good clinical practice (GCP E6 (R2)).

#### 9.2. Evaluation of the risk-benefit ratio

Moxidectin is a well-known, FDA-approved drug against onchocerciasis and has little and mainly mild adverse events (headache, abdominal pain etc.). All community members enrolled in the study will benefit from a clinical examination and a treatment against STHs. All participating subjects remaining positive for *S. stercoralis* will be treated with ivermectin (according to WHO recommendations).

#### 9.3. Subject information and consent

Community meetings allowing for open exchange will be organized in every study locality where a prescreening for identification of positive cases is to be conducted. The purpose and procedures, the benefits and risks of the study will be explained in order to make sure that all community members are at the same level in terms of information. All participants will be individually informed about benefits and risk associated to the trial. They will have sufficient time for reflection of their own participation.

All eligible adults ( $\geq$ 18, <66) will be asked to sign a written informed consent sheet. They will have sufficient time for reflection of their own participation. They will then be asked to sign a written informed consent sheet. In case the person is illiterate, an impartial witness that can read and write has to sign the consent and the illiterate participant to give a thumb print.

Information sheets are printed in English Lao and Khmer and will additionally be verbally translated into local languages during community meetings. To all participants a signed copy of the informed consent form will be given. Participation is voluntary and all participants have the right to withdraw from the study at any given point in time with no further obligations. Participation itself will not be awarded with compensation. However, transport and meals will be covered and free treatment of all diagnosed worms will be provided.

#### 9.4. Subject confidentiality

The obtained data will be handled strictly confidentially. Only members of the study team will have access to the data.

Screened patients will be listed in a confidential "subject screening log". Enrolled patients will be listed in a confidential "subject enrolment log" and attributed a unique study number; this document will constitute the only source to decode the pseudonymized data and will only be accessible to the local principal investigator. Data analysis will be conducted with pseudonymised data and reporting of findings will be fully anonymised; personal data will be coded for data analysis. No names will be published at any time, and published reports will not allow for identification of single subjects. Confidentiality and anonymity will be ensured Page **35** of **45** 

throughout the entire research project. All databases will be password secured. Subjectspecific information may be provided to other appropriate medical personnel only with the subject's permission.

The investigators have all been trained in GCP. None of the investigators declare to have any conflicts of interest.

#### 9.5. Subjects requiring particular protection

This study will be carried out in adults, since *S. stercoralis* infection occurs often in adults; hence this age group is at high risk of infection. Pharmacokinetic, dose-finding and non-inferiority studies have not been conducted to date in this population. Our trial will provide more evidence and pave the further way for a safe and effective treatment of strongyloides infections in adults.

#### 9.6. Other aspects

We will include one group of adults treated with placebo in each of the arms. However, this group will be treated with a standard treatment of a single dose ivermectin (200  $\mu$ g/kg) at the end of the study (already 3-4 weeks later); hence this does not cause any medical concern. Considering all security measures (clinical, physical and biochemical exams) set up for inclusion of trial participants, any person showing an unfavorable medical condition will not be included in the trial. Hence we believe that a treatment delay of 3-4 weeks is not expected to cause any problem. Of note, populations at risk are in general treated only in yearly intervals to reduce morbidity from chronic infections within MDA campaigns of national control programs.

## 10. Data management

The investigators are responsible for an adequate data quality. Prior to the initiation of the study, a short investigators meeting will be held with the investigators and their study coordinators and a member of the Swiss TPH. This meeting will include a detailed discussion of the protocol, performance of study procedures, CRF completion, specimen collection and diagnostic methods.

#### 10.1. Data collection

The data produced from this research project will fall into the following categories:

- 1. Eggs/Larvae counts of hookworm, *Ascaris lumbricoides* and *Trichuris trichiura* and *S. stercoralis* found in participants' stool, soil or water samples using either the Kato-Katz or the Baermann technique before (baseline; stool, soil, water) and after (follow-up; stool) treatment.
- 2. Personal information such as name, age and gender of trial participants.
- Anthropometric and clinical characteristics of the trial participants collected using the study's CRF such as weight, height, blood pressure, temperature, any abnormal medical condition or chronic disease.
- 4. Number and type of adverse events registered in the CRF and actively probed for 3 and 24 hours after treatment. The same data will be collected during the collection of the follow-up, 28 days after treatment.
- Pharmacokinetic parameters such as Cmax, AUC, or tmax analyzed from capillary or venous blood sampling at 0, 2, 4, 8, 24, and 72 hours, 7 and 28 days post dosing or in between 0 and 28 days post dosing.
- 6. Questionnaire: Record of the socioeconomic data of each participant's household

Data from categories 1-5 will be both paper-captured and directly into tablets using CommCare HQ (Digmagi, Inc., Cambridge, MA). CommCare HQ is a routine data management system ensuring complete, consistent and reliable data entry. For quality assurance error, range and consistency checks will assessed. 15% of data will be controlled by standard operating procedure, any discrepancies will be corrected by consulting the hard copy. If more than 1% of the double entered data display discrepancies, all data in categories 2-4 will be double entered by two independent people for quality assurance and verified as described.

Data entered into CommCare HQ databases will only be accessible to authorized personnel directly involved with the study by use of a password. It will directly be saved on the personal, password-protected laptop of one of the Co-PIs and uploaded to a server hosted at Swiss TPH, Basel. Data in category 1-4 will be saved both in .xlsx and .csv.

Data from categories 6 will be captured by software only. All categories will be merged into a single master filed saved in .xlsx and .csv. Data will then be analyzed as described in section 7. PK parameters (category 5) derived from analyzing micro blood and whole blood samples will be merged and saved as a .xlsx, .txt or/ and .m file.

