The slides from the Baermann and Kato-Katz thick smears will be analyzed under a microscope by experienced technicians and a subsequent independent quality control of sample results (approximately 10%) will be conducted. *S. stercoralis* larvae will be counted quantitatively and eggs recorded for the different helminths species separately and qualitatively assigned as egg positive or negative. Results are considered correct if the following tolerance margin is not exceeded: (i) No difference in presence/absence *S. stercoralis*, (ii) egg/larvae counts are +/-10 eggs/larvae for counts <100 eggs/larvae or +/-20% for counts >100 eggs/larvae (for each species separately) [30]. In case discrepancies above the tolerance margin are noted in one or more slides, all slides are re-read by the local technicians. The new results are discussed, so that in case of discordant results, slides can be re-evaluated to reach consensus. Infection intensity expressed as the arithmetic and geometric mean egg/larvae count per gram of stool will be calculated for each treatment arm. All microscopically analyzed Baermann samples as well as the Kato-Katz thick smears will be destroyed within one day (after passing the quality control).

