#### 4.3.4. Assessment of efficacy after treatment

The efficacy of the treatment will be determined 28 days post-treatment by collecting another three stool samples, which will be microscopically examined for *S. stercoralis* applying each duplicate Baermann technique as well as for potential co-infection with *A. lumbricoides*, *T. trichiura* and hookworm eggs using each duplicate Kato-Katz thick smears on two stool samples.

Participants will be considered *S. stercoralis* cured if no larvae have been found in any of the stool samples. Infection was calculated as larvae per gram stool. LPG will be assessed by calculating the mean of the larvae counts from the three duplicate Baermann assays and adjusted to the previously weighted used amount of stool sample. At the end of the study (day 21) all participants remaining positive for *S. stercoralis* will be treated with ivermectin (200  $\mu$ g/kg), the current standard drug against *S. stercoralis* [9].

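### Section 10.1's full double-entry step covers categories 2-4 only, so the larval counts behind cure and LRR get no full re-entry when the discrepancy trigger is met

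*Combined protocol and SAP*

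**What the plan says.** Section 10.1 sorts the data into six categories. Category 1 is the egg and larvae counts "found in participants' stool, soil or water samples using either the Kato-Katz or the Baermann technique before (baseline; stool, soil, water) and after (follow-up; stool)", where before and after are relative to dosing. Category 2 is personal information, 3 is anthropometric and clinical data, 4 is adverse events, 5 is pharmacokinetics and 6 is the household questionnaire.

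Capture is the same for the first five: "Data from categories 1-5 will be both paper-captured and directly into tablets using CommCare HQ". Category 6 is captured by software only.

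The checks in Section 10.1 come in three steps:
- A general step: "For quality assurance error, range and consistency checks will assessed".
- A sample check: "15% of data will be controlled by standard operating procedure, any discrepancies will be corrected by consulting the hard copy". No category is named.
- An escalation: "If more than 1% of the double entered data display discrepancies, all data in categories 2-4 will be double entered by two independent people".

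Section 4.3.4 counts a participant as "cured if no larvae have been found in any of the stool samples". Sections 4.1 and 7.1 make cure rate the primary endpoint. Section 4.3.1 adds a laboratory check, in which "a subsequent independent quality control of sample results (approximately 10%) will be conducted", and has the slides destroyed within a day once they pass it.

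**The concern.** The escalation is the plan's answer to evidence that data entry is not reliable enough. As written, it re-enters names, heights and adverse events in full but not the counts from which cure and LRR are calculated. Nothing about how the data are captured explains this, since category 1 is on paper and tablet exactly as categories 2-4 are.

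The counts are also the data for which automatic checks help least. Zero and a small positive number are both plausible values, so a range check will not flag one entered in place of the other, and that is the kind of error that can change cure status. The laboratory check concerns slide reading, not transcription. Once the slides are gone, the paper record is the only reference for the database.

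At stake is misclassification of the primary outcome in both trials: the non-inferiority comparison in trial B and the dose-response curve in trial A.

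**Working it through.** **Scope of the rule against the endpoint.** No stated figure is in dispute on this point; it rests on reading the sections together.
- Counts are category 1 (10.1), and cure is computed from them (4.3.4).
- Full re-entry after the trigger applies to categories 2-4 (10.1). Categories 1, 5 and 6 are outside it.
- Section 4.3.1 (slide re-reading), Section 4.4 (data verified before the codes are released), Section 10.2 (investigators review and approve each CRF) and Section 11.1 (local monitor under a separate plan) all add assurance. None provides full second entry of the counts.

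**Volume.** Each participant gives 3 stools x 2 Baermann assays = 6 counts per time point, at 2 time points. With full attendance:
- Trial B: 350 x 6 x 2 = 4,200 counts.
- Trial A: 210 x 6 x 2 = 2,520 counts.
- Total: 6,720.

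If the 15% control falls on category 1 in proportion, it covers 630 of trial B's 4,200 counts and leaves 3,570.

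**Illustration of misclassification.** The documents give no error rate for counts, so one is assumed. Let e be the share of true-zero follow-up counts entered as positive, with errors independent. A truly cured participant has six zeros and is recorded as not cured with probability q = 1 - (1 - e)^6. If a proportional 15% of counts is corrected, e is replaced by 0.85e.

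| assumed e | q, no correction | q, after 15% correction |
|---|---|---|
| 0.1% | 0.6% | 0.5% |
| 0.5% | 3.0% | 2.5% |
| 1% | 5.9% | 5.0% |
| 2% | 11.4% | 9.8% |

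These are upper-type figures, because many entry errors do not turn a zero into a positive count.

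**Effect on the trial B comparison.** Section 7.2 assumes 89% cure in both arms, a 10-point margin and 154 evaluable per arm for 80% power. The Section 7.3 interval reproduces this: SE = sqrt(2 x 0.89 x 0.11 / 154) = 0.0357, 95% half-width 7.0 points, power 80.1%.

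If the same q applies in both arms and no failures are recorded as cures, both cure rates are multiplied by (1 - q), and so is their difference:
- *Difference.* At e = 1% without correction, a true 10-point difference becomes 10 x (1 - 0.0585) = 9.4 points, a shrinkage of about 0.6.
- *Level and precision.* At e = 1% after the 15% correction, the observed cure rate is 0.89 x (1 - 0.0499) = 84.6%. The SE is sqrt(2 x 0.846 x 0.154 / 154) = 0.0412 and the half-width 8.1 points. Power under equal true cure rates is about 68%.
- *Range.* After correction, power is about 79% at e = 0.1%, 74% at 0.5% and 60% at 2%.

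**The case against.** Four points can fairly be made for the plan.

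*The counts are not left unverified.* A reader might infer that they are. The documents do not support that. The 15% control excludes no category and corrects discrepancies from paper, the error, range and consistency checks are not limited to any category, investigators approve each CRF, a monitor is foreseen, and Section 4.4 keeps the blind until the data are verified. This stands. What is missing is full second entry at escalation, not all checking.

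*Category 1 may already be double entered.* The escalation sentence refers to double-entered data without saying which data those are. Counts could be the set double entered at the first step, with escalation extending this to categories 2-4. Alternatively, the range could be a slip, since the same section groups categories 1-4 when it describes file formats. Either reading is possible, but neither is stated. This argues for clarification and against any inference that the endpoint data were left out on purpose.

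*One mis-keyed count need not change cure status.* It does so only if a zero becomes positive in a participant whose counts are otherwise all zero, or if a sole positive becomes zero. Replacing one positive number by another leaves cure unchanged, although it still enters the LRR. This stands, and it is why the percentages above are upper-type.

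*The share misclassified is not a between-arm effect.* It is tempting to set 5.9% of participants against the 10-point margin. That comparison is wrong: trial B is double blind, so entry errors should be similar in both arms, and the difference moves by about 0.6 points. The 1% in Section 10.1 is also a trigger for unspecified data, not an error rate for counts.

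**Conclusion.** The gap is real but narrow. When more than 1% of double-entered data disagree, Section 10.1 as written gives full re-entry to categories 2-4 and not to the counts that carry the primary endpoint, and no other section supplies it. The rest of the checking remains in place.

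The size is unknown, because no entry error rate is given. Under an assumed 0.1% to 2% of true-zero follow-up counts entered as positive, about 0.6% to 11.4% of truly cured participants would be recorded as not cured, or 0.5% to 9.8% after a proportional 15% correction. This assumes independent errors, a 15% control spread evenly over category 1, and similar error rates in the blinded arms. The main consequence is then a lower observed cure rate and some loss of precision. Shrinkage of a true difference is slight; its direction favours non-inferiority, but at these rates it is not evidence that the decision in trial B would be wrong. Errors that record a failure as a cure are not quantified here.

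This is a data-management correction worth making. It changes no endpoint definition, sample size or decision rule.

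**What to change.** In Section 10.1, extend the escalation from categories 2-4 to categories 1-4, or state that category 1 is fully double entered from the start. In the same paragraph, say which data are double entered at the first step and which categories the 15% control and the 1% trigger refer to. Section 4.4 already requires verification before code release, so no new timing rule is needed.

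Under the first option, the cost arises only if the trigger is met: one further entry round of counts already on paper, at most about 6,700 Baermann counts over both trials (6,720 with full attendance), plus the Kato-Katz readings. The second option incurs that work in any case. Neither adds visits, samples or participants.

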# 10.2. Data handling and definition of source data - data entered directly in the Case Report Form

*Source Data* are the clinical findings and observations, laboratory data maintained at the study site. Source data are contained in source documents. Local authorities are allowed to access

the source data. Data will be entered directly into the case report forms. The CRF is considered as a *source document*.

A CRF will be completed for each subject enrolled into the clinical study. The investigators will review, and approve each completed CRF. The study CRF is the primary data collection instrument for the study. All data requested on the CRF must be recorded. All missing data must be explained. If a space on the CRF is left blank because the procedure was not done or the question was not asked "N/D" will be entered. If the item is not applicable to the individual case "N/A" will be written. All entries will be printed in black ink. All corrections must be initialed and dated.

The study site (National institute of Laos) will retain a copy of the CRF to ensure that local collaborators can provide access to the *source documents* to a monitor, auditor, or regulatory agency while a copy of the CRF will be taken to Swiss TPH.

Digital copies along with the databases will be transferred to the Swiss TPH after a Material Transfer Agreement has been signed by both the Swiss TPH and National institute of Laos (see Appendix). All data is expected to not exceed 5 GB.

#### **10.3.** Definition of reference language – translation of study documents

- Protocol: Master document in English, all further language versions are translations thereof.
- CRF: Master document in English, all further language versions are translations thereof.
- ICF: Master document in English, all further language versions are translations thereof.

#### 10.4. Storage and preservation

After the study has been completed all samples will be destroyed. Data and related material will be preserved for a minimum of 15 years to enable understanding of what was done, how and why, which allow the work to be assessed retrospectively and repeated if necessary. Essential infrastructure such as lockable cabinets for safe storage of hardcopy data will be made available. Storage and backup will be in three places: personal password-protected laptops of [name], [name], [name] and [name], Swiss TPH shared server and SWITCHdrive (a cloud storage supported by University of Basel). To the shared server and SWITCH drive only the above mentioned study team has access. Electronic data files and archiving conditions will be made strictly confidential by password protection.

